#### **7.6. Subgroups**

The following subgroups based on baseline characteristics and stratification factors as reported by the Investigator on the CRF will be explored for primary and secondary efficacy endpoints. Summary tables will be provided for the ITT population. Forest plots will be provided for hazard ratios/odds ratio as applicable.

- Age category
  - $< 65$  years
  - $\geq 65$  years
- Sex
  - Male
  - Female

- Race
  - Asian
  - Black or African American
  - White
  - Rest of the races reported/Not Reported
- Geographic Regions
  - US or Canada or Europe or Australia or New Zealand
  - Latin America or Asia
- ECOG Performance status at baseline:
  - 0
  - 1
  - Missing
- KPS (%) at baseline:
  - 100-90
  - 80-70
  - Missing
- IMDC prognostic score per CRF:
  - Poor
  - Intermediate
- IMDC prognostic score per IxRS:
  - Poor
  - Intermediate
- Current histology types by archival tissue or biopsy (per cancer history CRF):
  - Clear cell
  - Papillary
  - Chromophobe
  - Sarcomatoid
  - Other
- Current disease stage per AJCC criteria (per cancer history CRF):
  - Stage III
  - Stage IV
  - Other
- Prior Nephrectomy
  - Yes
  - No

- Number of organs with target and non-target lesions per BIRC
  - 1
  - 2-3
  - 4-5
  - $\geq 6$
- Baseline SoD (mm) of target lesions per BIRC
  - $<$  Median
  - $\geq$  Median
- Visceral Liver Metastasis at baseline
  - Yes
  - No
- Visceral Metastasis at baseline
  - Yes
  - No
- Bone Metastasis at baseline
  - Yes
  - No
- Tumor PD-L1 status
  - $\geq 1\%$
  - $< 1\%$
  - Indeterminate
  - Missing

## 8. SAFETY SUMMARIES

All safety analyses will be performed on data as described in [Section 4.5](#) for subjects in the Safety population. A few summaries may be generated on the P-Safety population. No formal statistical comparison between the two treatments arms is planned.

Safety and tolerability will be assessed by the incidence of treatment emergent-adverse events (TEAEs), changes in laboratory parameters and vital signs from baseline, KPS, and ECOG PS.

An Independent Data Monitoring Committee (IDMC) will monitor safety of the subjects during the study on a regular basis. The committee will operate independently from the Sponsor and the clinical Investigators.

The primary responsibility of the IDMC is to review the accumulating safety data on a regular and an ad hoc basis and make recommendations to the Sponsor regarding the continued conduct

of the study. Safety data will be provided at regular intervals to the IDMC in the form of summary reports or data listings from the Sponsor (blinded) or its designated representative (unblinded).

Details regarding IDMC membership, schedule and format of meetings, format for presentation of data, access to interim data, mode and timing of providing interim reports to the IDMC, and other issues relevant to committee operations are described in the IDMC charter.

The IDMC members will use their expertise, experience, and judgment to evaluate the safety data from the trial and to recommend to the Sponsor whether the trial should continue or be stopped early for safety. No formal statistical rules recommending early stopping for safety are planned.

## **8.1. Adverse Events**

Adverse event terms recorded on the CRF will be mapped to preferred terms and system organ class using the MedDRA. The severity of AEs will be measured by CTCAE version 5.0 (Common Terminology Criteria for Adverse Events [CTCAE] Version 5.0 2009). The Investigator will judge each event to be “not related” or “related” to each study treatment component. Adverse events related to study treatment summaries will include all events that are judged to be related to at least one treatment component in the respective study arms.

A TEAE is defined as any event with an onset date on or after the date of the first dose of study drug or any ongoing event on the date of the first dose of study drug that worsens in severity after the date of the first dose of study drug.

Unless otherwise specified, only TEAEs with an onset date (or date of increase in severity) through the end of the relevant safety observation period (see [Section 4.5](#)) will be tabulated in summary tables.

All deaths starting at any time after informed consent, irrespective of when they occur, are recorded in the CRFs as Grade 5 AEs. However, only those associated with an event starting after informed consent through 100 days after the date of the decision to discontinue the last component study treatment (or starting at any time after informed consent and judged to be related to study treatment) require reporting them as an SAE.

For the purpose of calculating treatment emergence and inclusion in summary tables, incomplete onset dates will be imputed as detailed in [Appendix A](#).

An overall summary of adverse events will be provided with the number and percent of subjects who experienced the following types of events during the standard safety observation period

(unless otherwise noted as “at any time” or “during the extended safety observation periods” below) in each study treatment arm. Unless specified explicitly otherwise, the related criteria will be with respect to the study treatment regimen (at least one treatment component in the treatment regimen meeting the criteria) for the below summaries:

- Subjects with a TEAE
- Subjects with a Related TEAE
- Subjects with a Serious TEAE
- Subjects with a Serious Related TEAE
- Subjects with a Worst-Grade 3 or 4 TEAE
- Subjects with a Worst-Grade 3 or 4 Related TEAE
- Subjects with a Worst-Grade 3 TEAE
- Subjects with a Worst-Grade 3 Related TEAE
- Subjects with a Worst-Grade 4 TEAE
- Subjects with a Worst-Grade 4 Related TEAE
- Subjects with a Grade 5 TEAE (all deaths) at any time after first dose date and in the below categories:
  - ❖ ≤ 30 days after last dose of study treatment
  - ❖ ≤ 30 days after last dose of study treatment and not causally related to PD
  - ❖ > 30 days after last dose of study treatment
  - ❖ > 30 days after last dose of study treatment and not causally related to PD
  - ❖ ≤ 100 days after last dose of study treatment
  - ❖ ≤ 100 days after last dose of study treatment and not causally related to PD
  - ❖ > 100 days after last dose of study treatment
- Subjects with a Related Grade 5 TEAE at any time after first dose date and those in the below categories:
  - ❖ ≤ 30 days after last dose of study treatment
  - ❖ ≤ 30 days after last dose of study treatment and not causally related to PD
  - ❖ > 30 days after last dose of study treatment
  - ❖ > 30 days after last dose of study treatment and not causally related to PD
  - ❖ ≤ 100 days after last dose of study treatment
  - ❖ ≤ 100 days after last dose of study treatment and not causally related to PD
  - ❖ > 100 days after last dose of study treatment
- Subjects with a TEAE leading to dose modification (reduction or hold/delay)
- Subjects with a TEAE leading to dose reduction
- Subjects with a TEAE leading to dose hold/delay

- Subjects with TEAE leading to discontinuation:
  - Of at least one treatment component
  - Of all treatment components due to the same AE
  - Of cabozantinib/placebo
  - Of nivolumab
  - Of ipilimumab
- Subjects with Related TEAE leading to discontinuation:
  - Of at least one treatment component
  - Of all treatment components due to the same AE (note: the TEAE has to be related to all treatment components)
  - Of cabozantinib/placebo only
  - Of nivolumab only
  - Of ipilimumab only
- Subjects with TEAE leading to discontinuation and TEAE is not related to treatment and not causally related to disease under study:
  - Of at least one treatment component
  - Of all treatment components due to the same AE
  - Of cabozantinib/placebo only
  - Of nivolumab only
  - Of ipilimumab only
- Subjects with TEAE leading to discontinuation and TEAE is not related to treatment and is causally related to disease under study:
  - Of at least one treatment component
  - Of all treatment components due to the same AE (note: the TEAE has to be causally related to disease under study for all treatment components)
  - Of cabozantinib/placebo only
  - Of nivolumab only
  - Of ipilimumab only
- Subjects with immune-mediated TEAE up to extended safety observation period

The following summaries of AEs will be provided in general for standard observation period for subjects in the Safety population unless indicated otherwise:

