## **8 SAFETY**

### **8.1 Adverse Events and Laboratory Abnormalities**

#### **8.1.1 Adverse Events**

An AE is any untoward medical occurrence in a patient or clinical investigation subject who has been enrolled in a clinical study and who may have been administered an investigational product, regardless of whether or not the event is assessed as related to the study treatment. An AE can therefore be any unfavorable and unintended sign (including an abnormal laboratory finding), symptom, or disease temporally associated with the use of an investigational product, regardless of whether or not the event is assessed as related to the investigational product. This requirement

CONFIDENTIAL

includes specific events or symptoms associated with cancer progression or general clinical deterioration to ensure potential toxicities are not overlooked. Radiographic progression without associated clinical sequelae is not considered an AE: terms such as ‘disease progression’ should be avoided. Pre-existing medical conditions that worsen during a study will be recorded as AEs. Abnormal laboratory values, ECG findings, or vital signs are to be recorded as AEs if they meet the criteria described in [Section 8.1.2](#).

All untoward events that occur through 30 days (100 days for SAEs and certain other events [[Table 8-1](#)]) after the date of the decision to permanently discontinue study treatment (defined as the later of the date of the decision to discontinue all study treatment or the date of the last dose of any study treatment) are to be recorded by the investigational site. Further details are provided in [Appendix H](#).

At each scheduled and unscheduled visit, AEs are to be identified and assessed based upon study procedures, routine and symptom-directed clinical investigations, and subject query/report.

Assessment of the relationship of the AEs to individual study drug by the Investigator will be based on the following two definitions:

- **Not Related**: An event is assessed as not related to study drug if it is attributable to another cause and/or there is no evidence to support a causal relationship.

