## **8.2        Serious Adverse Events**

### **8.2.1      Definitions**

The SAE definition and reporting requirements are in accordance with the International Conference on Harmonization (ICH) Guideline for Clinical Safety Data Management: Definitions and Standards for Expedited Reporting, Topic E2A.

An SAE is defined as any untoward medical occurrence that at any dose

- Results in death.
- Is immediately life-threatening (ie, in the opinion of the Investigator, the AE places the subject at immediate risk of death; it does not include a reaction that, had it occurred in a more severe form, might have caused death).
- Requires inpatient hospitalization or results in prolongation of an existing hospitalization.
- Results in significant incapacity or substantial disruption of the ability to conduct normal life functions.
- Is a congenital anomaly or birth defect.
- Is an important medical event that may not be immediately life-threatening, result in death, or require hospitalization, but may be considered an SAE when, based upon appropriate medical judgment, it jeopardizes the subject or may require medical or surgical intervention to prevent one of the outcomes listed above.

As soon as an investigator becomes aware of an AE that meets the criteria for an SAE, the Investigator will document the SAE to the extent that information is available.

SAEs, regardless of causal relationship, must be reported to the Sponsor or designee within 24 hours of the Investigator's knowledge of the event by submitting the completed SAE report form and any other pertinent SAE information as indicated on the SAE Reporting form (or in the SAE Reporting form Completion Guidelines) and confirming the report was received. Forms for reporting SAEs and contact information will be provided to the study sites.

SAEs that must be recorded on an SAE Reporting form include the following:

- All SAEs that occur after informed consent and through 100 days after the date of the decision to permanently discontinue study treatment ie, the later of the date of the decision of

CONFIDENTIAL

Protocol XL184-313 Protocol Amendment 3.0  
Page 118 of 193

the Investigator to permanently discontinue study treatment or the date of the last dose of study treatment taken by the subject (or the date the subject is deemed to be a screen failure).

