- Any SAEs assessed as related to study treatment or study procedures, even if the SAE occurs more than 100 days after the date of the decision to permanently discontinue study treatment.

Note: If the subject does not meet the eligibility criteria during screening, then SAEs only need to be reported from the time the subject signs the informed consent until the day when the subject has been determined to not be eligible for study participation.

SAEs that occur after the initial consent and through 100 days after the date of the decision to permanently discontinue study treatment must also be recorded on the CRF page.

The minimum information required for SAE reporting includes identity of investigator, site number, subject number, and an event description. Other important information requiring timely reporting are the SAE term(s), the reason why the event is considered to be serious (ie, the seriousness criteria), and the Investigator's assessment of the relationship of the event to study treatment. Additional SAE information including medications or other therapeutic measures used to treat the event, action taken with the study treatment because of the event, and the outcome/resolution of the event will be recorded on the SAE form.

In all cases, the Investigator should continue to monitor the clinical situation and report all material facts relating to the progression or outcome of the SAE. Furthermore, the Investigator may be required to provide supplementary information as requested by the Sponsor's Drug Safety personnel or designee.

When reporting SAEs, the following additional points will be noted:

- When the diagnosis of an SAE is known or suspected, the Investigator will report the diagnosis or syndrome as the primary SAE term, rather than as signs or symptoms. Signs and symptoms may then be described in the event description.
- Death will not be reported as an SAE, but as an outcome of a specific SAE, unless the event preceding the death is unknown. Terms of "Unexplained Death" or "Death from unknown origin" may be used when the cause is unknown. In these circumstances the cause of death must be investigated and the diagnosis amended when the etiology has been identified. If an autopsy was performed, the autopsy report should be provided.

CONFIDENTIAL

Protocol XL184-313 Protocol Amendment 3.0  
Page 119 of 193

- While most hospitalizations necessitate reporting of an SAE, hospitalizations that do not require SAE reporting are as follows:

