#### **9.4.1 Adverse Events**

Adverse event terms recorded on the CRFs will be mapped to preferred terms using the Medical Dictionary for Regulatory Activities (MedDRA). The Investigator will classify the severity of AEs using the CTCAE v5 and will judge each event to be “not related” or “related” to study treatment.

A treatment emergent adverse event (TEAE) is defined as any event that begins or worsens on or after date of first dose of study treatment. Only TEAEs with an onset date prior to date of decision for treatment discontinuation (the later of the date of the decision of the Investigator to permanently discontinue study treatment or the date of the last dose of study treatment taken by

CONFIDENTIAL

the subject) + 30 days (+ 100 days for SAEs and certain other AEs; [Section 8.3](#)) will be tabulated in summary tables.

The frequency and percentage of subjects with TEAEs will be tabulated for overall incidence by system organ class and/or preferred term by treatment arm. Related TEAEs, serious TEAEs, related serious TEAEs, high-grade TEAEs, Grade 5 TEAEs, and TEAEs resulting in study treatment discontinuation will be similarly summarized. Summaries by worst reported severity for each event within a subject will also be provided.

At each level of summarization, a subject will be counted only once for each AE preferred term he/she experiences within that level (ie, multiple episodes of events with the same preferred terms will be counted only once).

All reported subject deaths will be summarized by treatment group, cause of death, and relationship to study treatment.

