### **4.5.1. Standard Period**

The standard safety observation period is the interval from the first dose date of study treatment to the earliest of:

- Date of last dose of last component of study treatment + 30 days, or
- Date of death, or
- Date subject withdrew consent for non-interventional study assessments, or
- Data cutoff date for analysis under consideration.

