### **4.5.2. Extended Period**

To evaluate the incidence of adverse events of interest (AESIs) associated with study treatment, extended observation period is defined as the interval from the first dose date of study treatment to the earliest of the following:

- Date of last dose of last component of study treatment + 100 days, or
- Date of death, or
- Date subject withdrew consent for non-interventional study assessments, or
- Data cutoff date for analysis under consideration.

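### The SAP's SAE tables stop at last dose + 30 days where Protocol 9.4.1 runs to + 100 days, so late non-fatal, non-AESI SAEs are not tabulated by arm, and the departure is not declared

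*SAP*

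**What the plan says.** **Protocol.** Section 9.4.1 is a rule about what enters the summary tables. The window is the later of the discontinuation decision or the last dose, plus "30 days (+ 100 days for SAEs and certain other AEs". The cross-reference for the other AEs is to Section 8.3, the AESIs. Collection matches this. Section 8.1.1 requires recording of "All untoward events that occur through 30 days (100 days for SAEs and certain other events", and Section 8.2.1 covers "All SAEs that occur after informed consent and through 100 days after the date of the decision to permanently discontinue study treatment". Section 8.2.1 adds that SAEs "through 100 days after the date of the decision to permanently discontinue study treatment must also be recorded on the CRF page".

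**SAP.** Section 4.5.1 ends the standard safety observation period at the earliest of "Date of last dose of last component of study treatment + 30 days", death, withdrawal of consent for non-interventional assessments, or data cutoff. Section 4.5.2 provides a 100-day period with a narrower purpose: "To evaluate the incidence of adverse events of interest (AESIs) associated with study treatment, extended observation period is defined". The overall summary in Section 8.1 counts subjects "who experienced the following types of events during the standard safety observation period", apart from rows marked otherwise. The lead-in to Table 15 reads: "The following summaries of AEs will be provided in general for standard observation period for subjects in the Safety population unless indicated otherwise".

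**Companion point.** Protocol 9.1.3 places anyone given any cabozantinib in error in the experimental arm. SAP 3.3 analyses by actual treatment, but allows subjects who received both treatments in error to be left out and only listed.

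**The concern.** The protocol gives the 100-day window to two classes, SAEs and AESIs. The SAP carries it over for AESIs only. The SAP also counts from last dose, where the protocol counts from the later of last dose and the discontinuation decision.

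In a double-blind add-on trial, SAE frequency by arm is a main basis for judging what cabozantinib adds to nivolumab and ipilimumab. If the SAP is followed as written, a tabulation that the protocol specifies would not be produced for part of the SAEs. That part can include cabozantinib risks that Protocol 6.6.2.1 names but the AESI list in Table 8-1 does not, such as GI perforation, fistula and wound healing complications. The protocol describes these as less frequent, and their share of late SAEs is not given. The class also includes events of other causes, among them symptoms of progression, which Protocol 8.1.1 counts as AEs.

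**Working it through.** No power or alpha calculation is involved. The check is a comparison of texts plus date arithmetic.

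**1. Which outputs are affected.** In the SAP 8.1 overall summary, the rows for serious TEAEs and for serious related TEAEs carry no note of a longer window, so the standard period applies: 2 rows. In Table 15, SAEs and related SAEs each appear by system organ class and preferred term, and again by preferred term alone, with no note: 2 × 2 = 4 summaries. Total: 2 + 4 = 6.

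**2. What is already covered beyond day 30.**
- Grade 5 events: at any time and up to 100 days (SAP 8.1 and Table 15).
- AESIs, including a row for serious AESIs: up to 100 days after last dose (SAP 8.3, Table 16).
- Immune-mediated TEAEs: the extended period (SAP 8.1).
- Non-fatal SAEs: data listing only (SAP 8.1).

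What remains is non-fatal, non-AESI SAEs with onset more than 30 days after last dose of the last component.

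**3. Length of the gap.** Count days from last dose of the last component. Let L be the days from that dose to the discontinuation decision, set to 0 if the decision came first.
- Protocol window for SAEs ends at day L + 100.
- SAP standard period ends at day 30 at the latest.
- Maximum gap = (L + 100) − 30 = 70 + L days.
- At L = 0: 70 days, or 70/100 = 70% of the post-treatment window.

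The documents give no distribution for L. As an assumed range for illustration only: L = 28 gives 98 days, and L = 84 gives 154 days. The 84 days are the 12-week interruption limit in Protocol 3.6.1, which the Sponsor may extend.

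**4. Truncation.** Let T be the days from last dose to the earliest of death, withdrawal of consent for non-interventional assessments, or cutoff, and assume that no event after T can be counted under either rule. Then the gap = min(L + 100, T) − min(30, T).
- T ≤ 30: gap 0.
- T = 60, L = 0: 60 − 30 = 30 days.
- T ≥ 100, L = 0: 100 − 30 = 70 days.
- Still on any component at cutoff: gap 0.

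**5. Would the SAP's own extended period close it?** It ends at last dose + 100, so the remaining gap would be (L + 100) − 100 = L days. The anchor has to change as well as the length.

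**6. Is the departure identified?** Protocol 9 lets the SAP carry modifications. SAP 4.8 says substantive changes from the protocol will be fully documented. The one change described there, in 4.8.1, is the expansion of the PFS population. The version history in Table 2 does not mention the SAE window or its anchor.

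**7. Safety population.** For a control subject who took both placebo and cabozantinib, Protocol 9.1.3 requires inclusion in the experimental arm, while SAP 3.3 permits exclusion and gives no criteria.

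**The case against.** The strongest reply is that nothing is hidden. The protocol hands analysis details to the SAP, the SAP prints its windows openly in 4.5 and 8.1, and Table 2 lists only primary reasons for each version, so its silence is weak evidence. Safety is descriptive, and whether a table window is a substantive change is a judgement. This stands in part. The departure is permitted and the rule is visible. What is missing is any statement that it differs from Protocol 9.4.1, and a reason for it.

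A second reply is that coverage exists elsewhere: fatal events, serious AESIs, the SAE listing, and the hospital, ICU and emergency-visit summaries for SAEs in SAP 7.5.10. Table 2 also moves the events-to-monitor section to a clinical safety plan that is not supplied. This rightly narrows the point to non-fatal, non-AESI SAEs. It does not remove it: a listing gives no frequency by arm, the resource summaries count days and visits rather than events by term, and the unseen plan cannot be assessed.

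Four stronger readings are tempting, and the documents do not support them.
- *All late SAEs are lost.* Fatal events and AESIs are tabulated to 100 days or beyond.
- *Every subject loses 70 days or more.* Death, withdrawal and cutoff shorten the gap, in some subjects to zero.
- *Events after cabozantinib stops while nivolumab continues are lost.* The SAP clock starts at the last component, so they remain inside the window.
- *The Safety population conflict runs both ways.* Protocol 9.1.3 does not address experimental-arm subjects given placebo in error, so there is no contradiction for them.

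**Conclusion.** The point holds as a should-fix inconsistency. Six SAE-specific outputs follow a shorter window and a different anchor from those in Protocol 9.4.1, and the SAP does not identify or justify this. Under the SAP as written, non-fatal, non-AESI SAEs starting more than 30 days after last dose are collected and listed but not tabulated by arm. The per-subject gap is bounded by 70 + L days and is smaller under the truncation set out above.

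This rests on reading the unmarked rows as belonging to the standard period. The SAP's general reference to a relevant observation period does not rescue them, because 4.5.2 ties the longer period to AESIs and the exceptions in 8.1 are marked row by row. The number of subjects or events affected cannot be derived. PFS, OS and type I error are untouched.

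The Safety population mismatch is minor and confined to control subjects who took both treatments.

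**What to change.** In SAP 4.5, 8.1 and Table 15, produce the two serious rows and the four SAE and related-SAE summaries over the Protocol 9.4.1 window: 100 days from the later of the discontinuation decision or last dose. Put them in a separate, clearly labelled block, so that a serious count cannot exceed the all-TEAE count within one table. State under SAP 4.8 that the general TEAE tables stay at 30 days from last dose. That statement is needed because 9.4.1 read literally would also bring late SAEs into those tables. Alternatively, keep the shorter SAE window and declare and justify it under SAP 4.8.

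In SAP 3.3, replace the optional exclusion with the Protocol 9.1.3 rule for control subjects who took any cabozantinib in error, or declare that departure too.

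The cost is SAP wording and a window flag in programming for six outputs. No new data are needed, since Protocol 8.2.1 already puts these SAEs on the CRF. The downside is that SAE rates rise by an unknown amount, some of it from events under subsequent anticancer therapy.
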